Amyloidopathy, Cholinopathy, Dopamine Responsiveness and Freezing of Gait in PD

NCT03647137

05/31/2022

Statistical Analysis Plan

In this proposal, the investigators present data suggesting that L-DOPA refractory freezing of gait (FoG) is associated with comorbid cholinopathy and amyloidopathy in Parkinson's disease.

The investigators propose to test the novel **hypothesis** that comorbid amyloidopathy may be a possible mechanistic factor underlying the poor response of FoG to dopaminergic therapy in advancing PD. In contrast, isolated cholinopathy (without amyloidopathy) would be expected to be associated with preserved dopamine responsiveness of FoG.

For this purpose, the investigators propose to perform detailed motor, including FoG, testing in PD patients "on" and "off" their dopaminergic medications and relate this to dopaminergic 11C- DTBZ, vesicular acetylcholine transporter 18F-FEOBV and amyloid 11C-PIB brain PET imaging in PD subjects with and without FoG.

Our statistical approach is to run a series of hierarchical ordinal logistic regression models, predicting freezing type (L-DOPA responsive, diminished L-DOPA responsiveness, and L-DOPA non-responsive) from dopaminergic (DTBZ), cholinergic (FEOVB), and amyloid (PIB) PET distribution volume ratio (DVR) of the striatum. The null model includes in it striatal DTBZ only. The FEOVB model adds a term for striatal cholinergic innervation. The interaction model, that most directly tests our comorbidity hypothesis adds an interaction term between FEOVB and PIB PET. Goodness of fit for the FEOVB model is compared against the null model, and the interaction model is compared against the FEOVB model.

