The premise of this project is that our preliminary data show that 'uncomplicated' PD—when still in a stage of predominant nigrostriatal dopaminergic denervation—does not have to be a very disabling disease *per se*. As a matter of fact, we found that gait speed in patients with predominant nigrostriatal degeneration is not significantly slower from healthy non-PD control subjects. However, our preliminary data show also that the emergence of non-dopaminergic extra-nigral pathologies in PD may result in significant disability due to FoG. If the association of amyloidopathy and dopamine refractoriness of FoG can be confirmed then this would provide a window for targeted interventions as these at risk-individuals could receive anti-amyloid targeted therapies that might prevent or improve disability in PD. A particular advantage of PD is that the low but symptomatic level of amyloidopathy provides a unique window of opportunity to intervene relatively early in the amyloid cascade. Serotonergic drugs that are already on the market may deserve further study as potential novel anti-amyloid investigational therapeutics, especially when administered very early in the disease course and well before the development of motor complications in PD. Such early and targeted anti-amyloid investigational therapy will critically depend on appropriate biomarker identification of subjects who are at risk of β -amyloid deposition.

The overarching goal of this study is to investigate the relationship between FoG and extranigral pathologies in PD and to test the hypothesis that comorbid amyloidopathy is a mechanistic factor underlying the poor response of FoG to dopaminergic therapy in advancing PD whereas FoG in cholinopathy alone is associated with preserved dopamine responsiveness. To achieve the goals of this project, patients with PD with and without FoG will undergo detailed FoG and gait motor testing in PD patients "on" and "off" their dopaminergic medication. Findings will be related to β -amyloid 11C-PIB, vesicular acetylcholine transporter 18FFEBBV, VMAT2 11C-DTBZ and, in a subset, SERT 11C-DASB brain PET imaging data. Interested subjects may also participate in an additional biomechanical/EMG of FoG and ocular function studies, to be performed on another day.

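### The only planned test of the cholinergic term on its own leaves amyloid out of both models, so it cannot inform the expectation for cholinopathy without amyloidopathy

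*Combined protocol and SAP*

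**What the plan says.** The Statistical Analysis Plan describes a sequence of ordinal logistic models for a three-level freezing type, graded by L-DOPA response. The starting point is amyloid-free: "The null model includes in it striatal DTBZ only". So is the next step: "The FEOVB model adds a term for striatal cholinergic innervation". PIB first enters in the interaction model, which "adds an interaction term between FEOVB and PIB PET"; no PIB main effect is named. Two comparisons are planned. In the first, "Goodness of fit for the FEOVB model is compared against the null model"; in the second, the interaction model is set against the FEOBV model.

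The hypothesis in the same section is conditional on amyloid: "isolated cholinopathy (without amyloidopathy) would be expected to be associated with preserved dopamine responsiveness of FoG". The Protocol Synopsis repeats it in the study goal: "whereas FoG in cholinopathy alone is associated with preserved dopamine responsiveness".

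The SAP says that the interaction model is the most direct test of the comorbidity hypothesis. It does not say how a better fit of the FEOBV model over the null will be interpreted, and it plans no estimate of the FEOBV effect at low amyloid.

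**The concern.** The expectation for cholinopathy is stated for patients without amyloid, but the one planned comparison that isolates a cholinergic term averages over all amyloid levels. There are two ways in which it can then be positive although isolated cholinopathy does nothing:

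- FEOBV and PIB are negatively correlated and PIB has an effect. The FEOBV coefficient then picks up part of the omitted PIB effect.
- Cholinergic loss matters only where amyloid is high, as the comorbidity hypothesis suggests. The averaged FEOBV slope is then non-zero even if the tracers are uncorrelated.

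In the second case, and in the first when the correlation is negative, the result reads as low FEOBV with worse L-DOPA response. On its face that conflicts with the expectation for isolated cholinopathy. A hypothesis that is true in both halves could thus produce a result that seems to speak against one of them.

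**Working it through.** **Inputs from the documents.** The terms of each model, the two comparisons and the three-level ordinal outcome, all from the Statistical Analysis Plan. The documents give no sample size, alpha, effect size or FEOBV–PIB correlation, so there is no planned figure to reproduce. They name only a goodness-of-fit comparison; a likelihood-ratio test is assumed here.

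**Assumptions.** Standardised tracers; three equal outcome groups; DTBZ log-odds −0.5 per SD, with DTBZ independent of the other tracers; PIB log-odds b = 0.7 or 1.2 per SD; true FEOBV effect zero; FEOBV–PIB correlation r = 0, −0.3, −0.5 or +0.3; N = 40, 80, 120; 1-df likelihood-ratio test at two-sided 5%; 800 data sets per setting.

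**Step 1: expected bias.** With PIB omitted, the FEOBV coefficient is roughly b × r, pulled somewhat towards zero in a logistic model.

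- 0.7 × (−0.3) = −0.21; simulated medians −0.19 to −0.20
- 0.7 × (−0.5) = −0.35; simulated −0.32 to −0.34
- 1.2 × (−0.3) = −0.36; simulated −0.28 to −0.30
- 1.2 × (−0.5) = −0.60; simulated −0.51 to −0.53

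**Step 2: rejection rate of FEOBV versus null, true FEOBV effect zero** (b = 0.7 / b = 1.2):

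| r | N=40 | N=80 | N=120 |
|---|---|---|---|
| 0 | 7.1% / 6.6% | 5.1% / 5.4% | 4.8% / 3.8% |
| −0.3 | 11.0% / 16.8% | 15.1% / 26.4% | 21.9% / 39.9% |
| −0.5 | 18.6% / 37.2% | 32.2% / 64.2% | 49.0% / 79.4% |
| +0.3 | 12.0% / 18.2% | 16.9% / 27.8% | 20.2% / 39.9% |

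At negative r nearly all rejections point to low FEOBV with worse response (10.4 of the 11.0 points at N=40, r = −0.3, b = 0.7). At r = +0.3 nearly all point the other way.

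**Step 3: PIB in both models** (DTBZ+PIB versus DTBZ+PIB+FEOBV), same data. Rejection is 6.0–7.4% (N=40), 5.1–6.5% (N=80) and 4.1–5.8% (N=120), and the median FEOBV coefficient is about zero.

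**Step 4: interaction-only truth.** Here FEOBV below its mean raises the log-odds by 2 per SD, but only when PIB exceeds 0.5 SD; isolated cholinopathy has no effect. Rejection at N = 40 / 80 / 120:

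| r | FEOBV versus null | FEOBV with PIB in both models |
|---|---|---|
| 0 | 12.9% / 19.8% / 25.8% | 12.5% / 19.5% / 26.0% |
| −0.3 | 22.2% / 41.0% / 52.1% | 15.0% / 25.1% / 31.6% |

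A PIB main effect is therefore not enough. In smaller runs (200 data sets per cell) in which the cholinergic effect acts only as amyloid rises, the PIB-adjusted test rejected in about 28–51%. The FEOBV slope at low PIB, from a model with both main effects and the interaction, rejected in about 6–8% of the same runs.

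**Simulation error.** With 800 data sets the standard error is √(0.05 × 0.95 / 800) = 0.8 points near 5% and √(0.5 × 0.5 / 800) = 1.8 points near 50%. With 200 data sets the latter is √(0.5 × 0.5 / 200) = 3.5 points.

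**The case against.** The strongest reply is that no passage ties the FEOBV-versus-null step to the isolated-cholinopathy expectation. The SAP points to the interaction model as the direct test of comorbidity. An unadjusted FEOBV association is a legitimate quantity, and finding it is an error only if the step was meant to hold amyloid fixed. This stands. A reader might infer that the trial will wrongly reject a true half of its own hypothesis; the documents do not support that, because they contain no decision rule that would turn this step into such a rejection.

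The dependence on correlation also stands. The SAP links both pathologies to refractory freezing, which is an association with the outcome and not a FEOBV–PIB correlation across the sample. The hypothesis itself presupposes some patients with cholinopathy and no amyloidopathy. The highest rates above need both the stronger correlation and the larger PIB effect.

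A reader might also infer that putting PIB into the base model cures the problem. It does so only if amyloid acts as a main effect; Step 4 shows that it fails under the kind of truth that the study proposes.

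What does not stand is that the interaction model makes the step harmless. FEOBV versus null is one of only two planned comparisons and the only one that isolates a cholinergic term. Inserting a PIB step after it would leave it unchanged.

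**Conclusion.** The concern holds in a limited form. As planned, the FEOBV-versus-null comparison cannot inform the expectation for cholinopathy without amyloidopathy, because it does not condition on amyloid.

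Under an amyloid main effect and negative FEOBV–PIB correlation, the spurious coefficient is about −0.2 to −0.5 per SD. That is an odds ratio for worse response of about exp(0.2) = 1.2 to exp(0.5) = 1.6 per SD lower FEOBV. With a main effect only, the error is about nominal at zero correlation, and a positive correlation reverses its direction. Under an interaction-only truth the step can be positive even at zero correlation. All rates depend on the assumed N, effect sizes, correlation and 5% test.

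This is a worthwhile, inexpensive improvement to the analysis and its interpretation. It does not show that the trial's conclusion will be wrong.

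**What to change.** Amend the model sequence in the Statistical Analysis Plan as follows:

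1. Keep FEOBV versus null, labelled as a descriptive result not adjusted for amyloid.
2. Add DTBZ+PIB versus DTBZ+PIB+FEOBV, and report the FEOBV odds ratio per SD with its 95% CI.
3. For the isolated-cholinopathy question, fit DTBZ, FEOBV, PIB and FEOBV × PIB, and report the FEOBV slope with its 95% CI at a low PIB value fixed in advance. State that this estimate, and not item 1, addresses the expectation for cholinopathy without amyloidopathy.

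The cost is SAP wording and two extra models on tracers already in the plan; no new scans are needed. The FEOBV intervals will be wider. At small samples the likelihood-ratio test of the low-PIB slope may be somewhat liberal (about 10–12% at n=40 in simulation), so the interval should carry the interpretation more than the p-value. The SAP's note on the serotonin sub-study already reports in the past tense that too few of those scans were available. If the main data have been examined, the added analyses should be dated and labelled accordingly.

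### The key model comparison has no PIB main-effect step, so an amyloid effect alone can pass as evidence of comorbidity

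*Combined protocol and SAP*

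**What the plan says.** The Statistical Analysis Plan describes its approach in these words: "run a series of hierarchical ordinal logistic regression models, predicting freezing type (L-DOPA responsive, diminished L-DOPA responsiveness, and L-DOPA non-responsive". Three striatal PET measures serve as predictors, the third being "and amyloid (PIB) PET distribution volume ratio (DVR) of the striatum". The models are then built up in three steps:

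- The first step holds the dopaminergic measure alone: "The null model includes in it striatal DTBZ only".
- The second step brings in FEOBV and still has no amyloid measure: "The FEOVB model adds a term for striatal cholinergic innervation".
- The third step is tied to the central hypothesis and is where amyloid first appears: "The interaction model, that most directly tests our comorbidity hypothesis adds an interaction term between FEOVB and PIB PET".

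Two comparisons of fit are planned. The second step is set against the first, and after that "the interaction model is compared against the FEOVB model".

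PIB is listed among the predictors, but it first appears at the interaction step. The plan does not say whether PIB also enters that model as a main effect, whether the DVRs are centred, or whether the interaction coefficient is tested on its own. The Protocol Synopsis adds nothing on the models.

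**The concern.** A test for interaction must compare two models that both contain the two main effects and differ only in the product term. Here the smaller model contains no amyloid at all. Whatever amyloid explains by itself is credited to the step that is meant to show amyloid acting together with cholinergic loss.

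This is the comparison that the plan singles out for its central hypothesis. A significant result would not tell a reader whether amyloid predicts L-DOPA-refractory freezing regardless of cholinergic status or only in combination with cholinopathy. The Protocol Synopsis wants to use a confirmed association to identify patients at risk for anti-amyloid treatment. The two explanations point to different groups of patients.

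**Working it through.** **1. The models as written.** The plan gives no sample size, alpha, effect size or DVR distribution, so there is no figure of its own to reproduce. The third model can be read in two ways:

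- (a) DTBZ + FEOBV + FEOBV×PIB, against DTBZ + FEOBV: 1 df.
- (b) DTBZ + FEOBV + PIB + FEOBV×PIB, against DTBZ + FEOBV: 2 df.

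**2. Reading (a), algebra.** Write FEOBV = m_F + s_F·f and PIB = m_P + s_P·p, with f and p standardised. Then

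FEOBV×PIB = m_F·m_P + m_P·s_F·f + m_F·s_P·p + s_F·s_P·f·p.

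The first term is a constant and the second is already in the model through FEOBV. What remains is s_F·s_P·(k·p + f·p), where k = m_F/s_F. If f and p are independent normal, the two parts are uncorrelated with variances k² and 1. PIB alone therefore accounts for k²/(k² + 1) of the new information:

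- k = 4: 16/17 = 94%
- coefficient of variation (CV) 15%, so k = 1/0.15 = 6.67: 44.4/45.4 = 98%
- k = 8: 64/65 = 98%
- FEOBV centred, so k = 0: 0%

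The meaning of the test thus depends on the origin of the scale. In one simulated data set of 60, used only as an illustration, the product-only test gave p = 0.27 with both DVRs centred and p < 0.0001 with the origin shifted by 1 to 16 SD. The product tested over a model with both main effects gave p = 0.32 at every origin.

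The sign can mislead as well. Low FEOBV with high PIB leading to non-response implies a negative product coefficient once both main effects are in the model. Under reading (a), a pure harmful PIB effect gives a positive one, through k·p. A goodness-of-fit comparison ignores the sign.

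**3. Reading (b).** The null hypothesis is that the PIB and product coefficients are both zero. A non-zero PIB coefficient is enough to reject it, on any scale.

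**4. Simulation.** All inputs are assumptions:

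- proportional-odds models with likelihood-ratio tests at 0.05
- a PIB main effect and a true interaction of zero
- log-odds of −0.5 per SD for DTBZ and for FEOBV
- DTBZ–FEOBV correlation 0.3, and PIB uncorrelated with both
- CV 15% for FEOBV and PIB, uncentred
- three outcome levels of roughly equal size
- 600 replicates per cell for N = 30 and 60, and 400 for N = 100 (Monte Carlo standard error at most about 2.5 points)

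| Freezers | PIB log-odds per SD | (a) product only | (b) PIB + product | product over DTBZ + FEOBV + PIB |
|---|---|---|---|---|
| 30 | 0 | 6.2% | 8.3% | 8.5% |
| 30 | 0.5 | 31.2% | 28.7% | 10.2% |
| 30 | 1.0 | 71.3% | 65.5% | 8.8% |
| 60 | 0 | 4.3% | 6.3% | 6.7% |
| 60 | 0.5 | 49.8% | 41.7% | 6.0% |
| 60 | 1.0 | 96.0% | 92.0% | 6.3% |
| 100 | 0.5 | 70.2% | 63.0% | 7.5% |
| 100 | 1.0 | 99.5% | 99.2% | 5.8% |

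At N = 60 and log-odds 1.0, a direct 1-df test of the PIB main effect rejects in 96.2% of trials. The planned comparison behaves almost like that test.

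**5. Sensitivity.**

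- With N = 60, log-odds 1.0, FEOBV CV 10–30% and PIB CV 8–20%: (a) 94.5–96.8%, (b) 92.8–94.5%, product over PIB 6.8–8.5%.
- With an outcome split of 50/25/25, FEOBV–PIB correlation −0.2, no FEOBV effect, mean/SD 4–8 and log-odds 0.8, the planned comparison rejects in 47–57%, 70–79% and 90–93% of trials with 30, 50 and 80 freezers. With log-odds 0.5 the figures are 26–32%, 36–46% and 51–59%. The product over PIB rejects in 8–10% at 30 freezers and 5–9% at 50–80.
- With both DVRs centred and only the product added, the rate falls to 6–12%.

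**The case against.** The strongest reply is that the hypothesis sets amyloid plus cholinopathy against cholinopathy alone and predicts nothing about amyloid without cholinopathy. An amyloid effect that is additive on the logit scale would also fit that contrast, and under reading (b) the joint step does test whether amyloid adds anything to FEOBV. This is a fair account of the hypothesis. It does not rescue the plan, which presents the step as a test of interaction; a joint test cannot show that.

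Three further points have some weight:

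- **Centring.** The plan is silent on it and does not rule it out. With centred DVRs, reading (a) nearly keeps its level. The conclusion would then hang on an unstated choice, and reading (b) fails either way.
- **Interpretation.** The paragraph may be shorthand, and an analyst could look at the interaction coefficient in a model that contains PIB. That would separate the effects, but the plan does not commit to it. False support is therefore a probability, not a certainty.
- **Power.** The correct test is weak in small samples. With an assumed PIB log-odds of 0.8 per SD and an interaction of 0.5, its power is about 21%, 35% and 53% at 30, 50 and 80 freezers, against 54%, 77% and 96% for the 2-df comparison. This is a real cost. The 2-df comparison owes much of its advantage to the PIB main effect, for which it also rejects when there is no interaction.

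**Conclusion.** The concern holds. The comparator for the key test omits PIB, so better fit than the FEOBV model does not show that amyloid and cholinergic loss act in combination. The text establishes this, and it does not depend on any simulated figure.

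The size does depend on assumptions about sample size, effect size, outcome split, correlation and DVR spread, because the documents give none of these. The rates should be read as illustrative. Where amyloid has a moderate to large effect of its own, the chance of a spurious finding runs from over a quarter to near certainty and grows with sample size. The product-only test on centred DVRs is the one exception, and the plan does not specify it.

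**What to change.** State four nested models, with all DVRs centred:

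- M0: DTBZ
- M1: M0 + FEOBV
- M2: M1 + PIB
- M3: M2 + FEOBV×PIB

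Test the comorbidity hypothesis as M3 against M2 (1 df). Report M2 against M1 separately as the amyloid main effect. Give the interaction estimate with its sign and confidence interval, because a non-significant M3-versus-M2 result in a small sample says little. The likelihood-ratio test is somewhat liberal at about 30 freezers (roughly 8–12% in the simulations), so the plan should also say how small-sample error will be handled.

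The cost is a change of wording and one more model fit on existing scans. The price is lower power for the interaction claim, as shown under the objection. The plan already reports in the past tense that too few DASB scans were obtained for analysis, so data collection may have been well advanced. If outcome data had been examined before the change, the revised test should be labelled post hoc.

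### The comorbidity hypothesis rests on a goodness-of-fit comparison with no calibrated rule; its false-positive rate can exceed 5%, with AIC at any sample size and with the likelihood-ratio test when freezers are few

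*Combined protocol and SAP*

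**What the plan says.** The Statistical Analysis Plan section of the combined document will "run a series of hierarchical ordinal logistic regression models", with a three-level outcome: "predicting freezing type (L-DOPA responsive, diminished L-DOPA responsiveness, and L-DOPA non-responsive"). Terms enter in steps:

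- The base model has DTBZ as its sole predictor.
- A second model brings in FEOBV as well.
- The third step is worded as follows: "The interaction model, that most directly tests our comorbidity hypothesis adds an interaction term between FEOVB and PIB PET".

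The decision step is a single sentence on goodness of fit. It first sets the second model against the base model, and then "the interaction model is compared against the FEOVB model". Neither this section nor the Protocol Synopsis names a fit criterion, test statistic, reference distribution, significance level or threshold. Neither says which of the two comparisons is confirmatory, and neither gives a sample size. (The SAP writes both FEOBV and FEOVB; FEOBV is used here.)

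**The concern.** Adding terms to a nested model cannot lower its maximised likelihood. A comparison of fit therefore needs a rule for how much improvement counts as evidence. Two common rules are AIC and the chi-square likelihood-ratio test (LRT). AIC is not built to hold a 5% error rate. The LRT holds it only in large samples, and an ordinal model with three or four PET terms fitted to few patients may be far from that.

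The listed outcome levels are all types of freezing. The Synopsis says that "patients with PD with and without FoG will undergo detailed FoG and gait motor testing", but there is no outcome level for non-freezers, so the usable sample is probably the freezers alone.

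At stake is the error rate of the study's main claim. The Synopsis says that confirmation of this association would open the way to anti-amyloid treatment for patients at risk.

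**Working it through.** The plan has no error rate or power figure to reproduce, so the check asks what error rate each plausible rule would give.

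**Inputs from the SAP:** three ordered outcome levels; a DTBZ model; a DTBZ + FEOBV model; an interaction model. Hierarchical is read as stepwise entry of blocks of terms. Read literally, the interaction model adds only FEOBV × PIB (1 df). If a PIB main effect enters with it, the step has 2 df. Both readings are computed.

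**Assumed, because the documents do not say:** 15 to 80 freezers; category shares in equal thirds or 50/25/25; PIB normal or skewed; LRT at 5%, or lower AIC wins.

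**AIC in large samples.** AIC prefers the larger model when the likelihood-ratio statistic exceeds 2 × df.

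- 1 df: P(χ²₁ > 2) = 0.157
- 2 df: P(χ²₂ > 4) = exp(−2) = 0.135

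**Finite samples.** Proportional-odds fits, 2,500 data sets per setting, all true slopes zero. The Monte Carlo standard error is √(0.07 × 0.93 / 2,500) = 0.5 points near 7% and √(0.20 × 0.80 / 2,500) = 0.8 points near 20%. Percentage of data sets in which the interaction model is preferred to the FEOBV model:

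| Freezers (assumed) | LRT, 1 df | LRT, 2 df | AIC, 1 df |
|---|---|---|---|
| 15 | 10.9–12.0 | 16.7–17.6 | 25.7–27.0 |
| 20 | 8.9–10.4 | 12.0–13.6 | 22.3–24.3 |
| 30 | 7.4–9.2 | 8.4–10.8 | 20.5–22.2 |
| 40 | 7.1–8.0 | 7.2–8.6 | 18.9–21.4 |
| 60 | 6.2–7.4 | 6.4–8.1 | 19.3–21.2 |
| 80 | 5.3–6.8 | 6.3–7.3 | 16.5–18.5 |

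AIC with 2 df runs from 29.4–32.0% at 15 freezers to 15.4–17.3% at 80. A separate simulation with a 50/30/20 split and normal PIB agrees for the LRT: 10.7–12.6% at 20, 8.7–9.8% at 30, 6.7–8.8% at 45, 6.5–7.2% at 60 and about 5.8% at 80.

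**Does calibration work?** The 1-df cut-off that gives 5% is 4.7–5.1 at 30 freezers and 4.0–4.4 at 80, against the nominal 3.84. With no PIB effect, a parametric bootstrap of 99 draws in 270 simulated studies brought the LRT from 8.9% to 4.4% at 30 freezers and from 8.1% to 5.2% at 45. The standard error near 5% is √(0.05 × 0.95 / 270) = 1.3 points. A further bootstrap simulation gave 3.8–5.5% at 30 and 45.

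**Which smaller model?** Suppose PIB has a main effect (assumed slope 0.8 per SD) and there is no interaction. Percentage of data sets in which the nominal 5% LRT favours the larger model:

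- PIB and FEOBV × PIB added to DTBZ + FEOBV (2 df): 42–93% across 20 to 80 freezers.
- FEOBV × PIB alone added to DTBZ + FEOBV (1 df): 7–13%.
- FEOBV × PIB added to DTBZ + FEOBV + PIB (1 df): 11.2–12.8% at 20, 8.5–8.8% at 30, 7.3–7.5% at 40, 6.4–7.0% at 60 and 5.9% at 80.

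Only the third isolates the interaction, and what remains is small-sample inflation. Calibrating the 2-df test under no PIB effect does not help: it still favoured the interaction model in 38%, 58% and 71% of studies at 30, 45 and 60 freezers (50/30/20 split, 600 studies per cell).

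**The case against.** **The rates are conditional.** The documents give no number of freezers and name neither AIC nor the LRT. A statistician could reasonably take a hierarchical comparison to mean an ordinary LRT at 5%; with 80 freezers its size is 5.3–7.3%, which few would dispute. The largest percentages under no PIB effect come from AIC, which the SAP does not mention. All of this stands. A reader might infer that the false-positive rate is well above 5% as a fact, and the documents do not support that.

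**BIC is another option.** With no PIB effect, a 50/30/20 split and 1,000 studies per cell, it favoured the interaction model in 16%/13% (1 df/2 df) at 20 freezers, 8.3%/5.6% at 30, 5.9%/3.7% at 45 and 4.2%/1.1% at 80. It is thus near or below 5% in the larger samples. But its error rate drifts with sample size, so it is not a 5% rule either.

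**Two comparisons.** A reader might infer that two tests at 5% give the comorbidity claim a family-wise error of 1 − 0.95² = 9.75%. They do not. The FEOBV versus null comparison contains no PIB term and cannot support a claim about amyloid. What remains is that the SAP should say which comparison is confirmatory. It already comes close by saying which model tests the hypothesis most directly.

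**Motive.** The Synopsis speaks of confirmation conditionally. Nothing in it shows that the investigators favour one result.

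**Conclusion.** The concern holds in conditional form and should be fixed. The SAP decides its central hypothesis by an unspecified comparison of fit. Under AIC, a null interaction term is preferred about 16% of the time (1 df) even in large samples; this needs no assumption about sample size. Under the chi-square LRT with no PIB effect, size is about 9–14% at 20 freezers, 7–11% at 30, 6–8% at 60 and 5–7% at 80. The excess is clear below about 45 freezers and small by 80.

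The LRT figures rest on assumed sample sizes, category shares and PIB distributions, and on only freezers having an outcome level. The choice of smaller model matters as much as the cut-off: unless PIB is already in it, evidence for a PIB main effect can pass as evidence for comorbidity. The size of that effect depends on the assumed slope of 0.8 per SD.

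**What to change.** Replace the goodness-of-fit sentence in the SAP with the following:

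- **Confirmatory comparison:** DTBZ + FEOBV + PIB against the same model plus FEOBV × PIB (1 df), named as the only confirmatory test. FEOBV versus null is descriptive.
- **Test:** the likelihood-ratio statistic with an upper-tail parametric-bootstrap p-value at the 5% level. Simulate freezing type from the fitted DTBZ + FEOBV + PIB model and refit both models at least 2,000 times. At p = 0.05 the simulation error is then √(0.05 × 0.95 / 2,000) = 0.5 points.
- **Failed refits:** a rule set in advance for refits that do not converge and for draws that lack an outcome category.
- **Not decision rules:** AIC and raw fit.

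The bootstrap checks above were run with no PIB effect. The team should repeat them for this comparison, with a PIB main effect, at its actual number of freezers.

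The cost is SAP wording and minutes of computing. The downside is slightly larger p-values and somewhat less apparent power than the uncalibrated test.
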